8.4 Main criteria

- To compare safety of oral Ciprofloxacin[®] tablets (Ciprofloxacin/Metronidazole) versus currently used Ciprofloxacin[®] Tablets & Metronidazole[®] tablets in pelvi-abdominal infections, either non-operative or post-operative following IV antibiotics.
- To compare efficacy of oral Ciprofloxacin[®] tablets (Ciprofloxacin/Metronidazole) versus currently used Ciprofloxacin[®] Tablets & Metronidazole[®] tablets in pelvi-abdominal infections, either non-operative or post-operative following IV antibiotics.

8.5 Other criteria

- To describe presence of any signs/symptoms of post-operative wound infection such as redness, fever or wound discharge.
- To describe presence of undesirable effects on total leukocyte count and liver enzymes (SGOT & SGPT) between baseline (visit 1) to End of study visit (Follow up 2 V)
- To compare the complete resolution, improvement, failure or relapse of Pelvi-abdominal infection between ciprofloxacin[®] versus combined treatment, based on pelvi-abdominal ultrasound and others
- To compare the number of days for complete healing of post-operative wounds between ciprofloxacin[®] versus combined treatment

8.6 Primary Safety analysis

A. Number of participants experiencing Serious Adverse Events (SAEs). [Time Frame: visit 1 to End of study visit].

- Frequency distribution (number & percent) of occurrence of SAEs necessitating a change or discontinuation of treatment. Chi² test will be used to determine p-value and significance between the 2 groups.

- Frequency distribution (number & percent) of type and severity of SAEs. Chi² test will be used to determine *p*-value and significance between the 2 groups.

B. Number of participants experiencing Adverse Events (AEs) leading to permanent discontinuation of the study drug. [Time Frame: visit 1 to End of study visit].

- Frequency distribution (number & percent) of causes of treatment discontinuations. Chi² test will be used to determine *p*-value and significance between the 2 groups.
- Frequency distribution (number & percent) of occurrence of AEs necessitating a change or discontinuation of treatment. Chi² test will be used to determine *p*-value and significance between the 2 groups.
- Frequency distribution (number & percent) of type and severity of AEs. Chi² test will be used to determine *p*-value and significance between the 2 groups.

8.7 Primary Efficacy analysis:

A. Complete resolution for Pelvi- abdominal infection based on pelvi-abdominal Ultrasound

- Frequency distribution (number & percent) of complete resolution for pelvi-abdominal infection. Chi² test will be used to determine *p*-value and significance between the 2 groups.

B. Complete healing of the post-operative wounds [Time Frame: Follow-up 1 V to End of study visit].

- Frequency distribution (number & percent) of complete healing of the post-operative wounds. Chi² test will be used to determine *p*-value and significance between the 2 groups.
- Frequency distribution (number & percent) of incomplete healing of the post-operative wounds. Chi² test will be used to determine *p*-value and significance between the 2 groups.
- Frequency distribution (number & percent) of no healing of the post-operative wounds. Chi² test will be used to determine *p*-value and significance between the 2 groups.

8.8 Secondary Safety analysis:

A. Presence of any signs/symptoms of post-operative wound infection such as redness, fever or wound discharge [Time Frame: visit 1 to End of study visit].

- Frequency distribution (number & percent) of presence of any signs/symptoms of post-operative wound infection such as redness, fever or wound discharge. Chi² test will be used to determine *p*-value and significance between the 2 groups.

B. Change in Total leukocytes count between baseline (visit 1) to End of study visit

- Descriptive analysis (mean, Standard Deviation, Median, Interquartile Range, Minimum and Maximum) of total leucocyte will be from baseline (visit 1) to End of study visit. Percent change will be calculated between baseline to End of study. Paired t-test will be used to determine p-value and significance between baseline and at the end of the study. Unpaired t-test will be used to determine the p-value and significance between Changes in total leucocyte between 2 groups.

C. Change in Liver enzymes (SGOT) between baseline (visit 1) to End of study visit

- Descriptive analysis (mean, Standard Deviation, Median, Interquartile Range, Minimum and Maximum) of Liver enzymes (SGOT) will be from baseline (visit 1) to End of study visit. Percent change will be calculated between baseline to End of study. Paired t-test will be used to determine p-value and significance between baseline and at the end of the study. Unpaired t-test will be used to determine the p-value and significance between Changes in Liver enzymes (SGOT) between 2 groups.

D. Change in Liver enzymes (SGPT) between baseline (visit 1) to End of study visit

- Descriptive analysis (mean, Standard Deviation, Median, Interquartile Range, Minimum and Maximum) of Liver enzymes (SGPT) will be from baseline (visit 1) to End of study visit. Percent change will be calculated between baselines to End of study. Paired t-test will be used to determine p-value and significance between baseline and at the end of the study. Unpaired t-test will be used to determine the p-value and significance between Changes in Liver enzymes (SGPT) between 2 groups.

8.9 Secondary Efficacy analysis:

A. Complete resolution, improvement, failure or relapse of Pelvi- abdominal infection

- Frequency distribution (number & percent) of complete resolution, improvement, failure or relapse for Pelvi- abdominal infection. Chi² test will be used to determine p-value and significance between the 2 groups.
- Frequency distribution (number & percent) of improvement for Pelvi- abdominal infection. Chi² test will be used to determine p-value and significance between the 2 groups.
- Frequency distribution (number & percent) of failure for Pelvi- abdominal infection. Chi² test will be used to determine p-value and significance between the 2 groups.

- Frequency distribution (number & percent) of relapse for Pelvi- abdominal infection. Chi² test will be used to determine p-value and significance between the 2 groups.

B. Days for complete healing of post-operative wounds after 8 days of treatment (Follow up 1 visit) & 15 days of treatment (Follow up 2 visit or End of study visit)

- Descriptive analysis (mean, Standard Deviation, Median, Interquartile Range, Minimum and Maximum) of days for complete healing versus combined treatment will be after 8 days of treatment (Follow-up 1 V) & 15 days of treatment (End of study visit). Percent change will be calculated between baseline to End of study. Paired t-test will be used to determine p-value and significance between baseline and at the end of the study. Unpaired t-test will be used to determine the p-value and significance between Changes in complete healing between 2 groups.

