4. Subjects who are willing to sign Informed Consent Form (ICF) and ready to comply with the protocol for the duration of the study

10.2.2 Exclusion Criteria:

Subjects presenting with any of the following will not be included in the study:

1. Subjects with a history of hypersensitivity to any of the active ingredients of the treatments used
2. Subjects who are receiving or received any other antibiotics during the previous two weeks, rather than IV treatment in the first post-operative 48 hours, mentioned in the protocol (Metronidazole injection plus third generation cephalosporin)
3. Subjects with Pelvi-abdominal infection and performed surgery after failure of oral antibiotics.
4. Subjects having surgeries such as colorectal surgeries, appendectomy and ovarian cystectomy
5. Subjects with any medical condition requiring the usage of the following medications:

- a. Drugs that induce microsomal liver enzymes, such as Phenytoin or Phenobarbital, may accelerate the elimination of metronidazole
 - b. Drugs that decrease microsomal liver enzymes activity, such as cefrimide, may prolong the half-life and decrease plasma clearance of metronidazole.
 - c. Administration of theophylline in combination with Ciprofloxacin may lead to cardiac arrest, seizures, status epilepticus, and respiratory failure
 - d. Administration of corticosteroids in combination with Ciprofloxacin may lead to tendinitis
 - e. Antacids containing magnesium and aluminum, supplements and other products containing calcium, iron or zinc as they reduce the effect of Ciprofloxacin.
 - f. Tizanidine because this may cause low blood pressure and sleepiness
6. Subjects with uncontrolled diabetes mellitus; FBG > 200 mg/ml
 7. Subjects with renal impairment (S. Creatinine > 1.5 mg/dL)
 8. Subjects with hepatic impairment (Child-Pugh Score B-C)
 9. Subjects with liver enzymes (SGOT, SGPT) > 2 times Normal range.
 10. Pregnant or breast feeding women

10.2.3 Discontinuation/Withdrawal of participants from the study:

Each participant has the right to withdraw from the study at any time.

In addition, the investigator may discontinue a participant from the study at any time if the investigator considers it necessary for any reason including:

1. Ineligibility (either arising during the study or retrospective having been overlooked at screening)
2. Significant protocol deviation
3. Significant non-compliance with treatment regimen or study requirements

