4. Disease progressions which requires discontinuation of the study medication or results in inability to continue to comply with study procedures.
5. Consent withdrawn by subject.
6. Lost to follow up
7. SAE or death
8. If a female subject becomes pregnant
9. Subjects which have Cholecystitis and it will be operated upon.

The reason for withdrawal will be recorded in the CRF. If the participant is withdrawn due to an adverse event, the investigator will arrange for follow-up visits or telephone calls until the adverse event has resolved or stabilized.

10.2.4 Assessments to be done:

1- Screening Visit Assessments:

- The enrollment period will be 12 months including the screening visit. Screening assessments will be completed and treatment will be initiated within visit 1.
- During this visit, patients will be screened for fulfillment of the inclusion and exclusion criteria and written informed consent will be obtained.
- Screening assessments will include physical examination, medical history, patient demographics, vital signs, concomitant medications, safety laboratory tests

(including Fasting Blood Sugar (FBS), Total leukocyte count, Liver enzymes (SGOT & SGPT), Total Bilirubin and S. Creatinine), Child-Pugh Score (for hepatic impairment) and, β -HCG (for females of child bearing potential only) and pelvi-abdominal Ultrasound & others.

- Presence of any signs/symptoms of post-operative wound infection such as redness, fever or wound discharge will be recorded (in case of post-operative subjects)

2- Follow-up 1 Visit:(Day 8):

- On-treatment assessments include physical examination, vital signs, AEs, SAEs, concomitant medication and study drug dosing compliance
- Days for complete healing will be checked
- Complete resolution, improvement, failure or relapse of Pelvi- abdominal infection
- Presence of any signs/symptoms of post-operative wound infection such as redness, fever or wound discharge will be recorded (in case of post-operative subjects)

3- Follow-up 2 Visit & End of study visit (Day 15):

- Assessments include physical examination for vital signs, AEs, SAEs, concomitant medication, and study drug dosing compliance
- Pelvi-abdominal Ultrasound and others will be done, if needed upon Physician's decision.
- Days for complete healing will be checked
- Complete resolution, improvement, failure or relapse of Pelvi- abdominal infection

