 - e. Antacids containing magnesium and aluminum, supplements and other products containing calcium, iron or zinc as they reduce the effect of Ciprofloxacin[®].
 - f. Tizanidine because this may cause low blood pressure and sleepiness
6. Subjects with uncontrolled diabetes mellitus; FBG > 200 mg/ml
7. Subjects with renal impairment (S. Creatinine > 1.5 mg/dL)
8. Subjects with hepatic impairment (Child-Pugh Score B-C)
9. Subjects with liver enzymes (SGOT, SGPT) > 2 times Normal range.
10. Pregnant or breast-feeding women

4 Medicinal Products:

- Ciprofloxacin[®] Tablets (Ciprofloxacin hydrochloride 500 mg & Metronidazole 500 mg)

5 Endpoints:

5.1 Primary Endpoints:

5.1.1 Primary Safety:

Incidence of serious/non-serious adverse events

5.1.2 Primary Efficacy:

- Complete resolution for pelvi-abdominal infection based on pelvi-abdominal ultrasound and others and/or clinical response
- Complete healing of post-operative wounds

5.2 Secondary Endpoints:

5.2.1 Secondary Safety:

- Presence of any signs/symptoms of post-operative wound infection such as redness, fever or wound discharge.
- Change in Total leukocytes count and Liver enzymes (SGOT, SGPT), between baseline (visit 1) to End of study visit (Follow up 2 visit)

5.2.2 Secondary Efficacy:

- Describe complete resolution, improvement, failure or relapse of pelvi-abdominal infection based on pelvi-abdominal ultrasound and others and or clinical response.
- Days for complete healing of post-operative wounds after 8 days of treatment (Follow-up 1 V) & 15 days of treatment (End of study visit) between the 2 groups

6 Assessment Schedule

Subjects will be enrolled for 12 months including screening visit

- Visit 1: Screening and treatment initiation visit, Day 0
- Follow-up 1 visit: Day 8 (+/-) 3 days
- Follow-up 2 visit & End of study visit: Day 15 (+/-) 3 days

7 Study Size:

Subjects having pelvi-abdominal infection, in post-operative period of pelvi-abdominal surgeries or acute conditions will be selected from the surgical department in Menoufia University Hospital and some subjects might be referred from other departments in Menoufia University Hospital such as and not limited to; the department of Gynecology and Obstetrics. Patients will be asked to participate in the study and sign the informed consent, then screening for inclusion and exclusion criteria will be done and recorded in the patient's medical records (either enrolled or screening failure).

7.1 Determination of Sample Size:

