9.4 Primary End Point

9.4.1 Primary Safety

Table 4 *Number and percent of Adverse Event necessitating a change or discontinuation of treatment among treatment groups*

	Group A (N=156)	Group B (N=156)	p-value
Total No of SAE, N (%)			
SAE1, N (%)			
SAE2, N (%)			
SAE3, N (%)			

Table 5 *Number and percent of Serious Adverse Event among treatment groups*

	Group A (N=156)	Group B (N=156)	p-value
Total No of SAE, N (%)			
SAE1, N (%)			
SAE2, N (%)			
SAE3, N (%)			

Table 6 *Number and percent of causes of treatment discontinuations among treatment groups*

	Group A (N=156)	Group B (N=156)	p-value
Total No of treatment discontinuations, N (%)			
Cause1, N (%)			
Cause2, N (%)			
Cause3, N (%)			

Table 7 *Number and percent of Adverse Event necessitating a change or discontinuation of treatment among treatment groups*

	Group A (N=156)	Group B (N=156)	p-value
Total No of AE, N (%)			
AE1, N (%)			
AE2, N (%)			
AE3, N (%)			

Table 8 *Number and percent of Adverse Event among treatment groups*

	Group A (N=156)	Group B (N=156)	p-value
Total No of AE, N (%)			
AE1, N (%)			
AE2, N (%)			
AE3, N (%)			

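### Primary safety part B is headed AE-caused permanent discontinuation, but its first test and Table 6 are not limited to AEs, and no table shell as labelled tests the headed quantity

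*SAP*

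**What the plan says.** The defined primary safety endpoint (SAP 5.1.1, Protocol 10.3.1) is "Incidence of serious/non-serious adverse events". Part B of the primary safety analysis (SAP 8.6, repeated in Protocol 10.7.6) is headed "Number of participants experiencing Adverse Events (AEs) leading to permanent discontinuation of the study drug".

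Three items follow, each with a chi-square comparison of the two groups. The second and third name adverse events explicitly. The first does not: it is "Frequency distribution (number & percent) of causes of treatment discontinuations".

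The SAP shells in 9.4.1 Primary Safety follow the items:

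- Table 6 is titled "Number and percent of causes of treatment discontinuations among treatment groups". Its first row is "Total No of treatment discontinuations, N" (%), followed by three placeholder cause rows, beside a p-value column.
- Table 7 is titled "Number and percent of Adverse Event necessitating a change or discontinuation of treatment among treatment groups". Table 4 has the same title with SAE rows.

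SAP 8.3.2 sets every test at the 5% level and calls p<0.05 statistically significant. Neither document defines treatment discontinuation.

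**The concern.** The test does not match its heading. If Table 6 counts stops for any reason, its total mixes tolerability with matters such as adherence and consent. Protocol 10.2.3 shows that the sponsor expects departures unrelated to adverse events, for example "Significant non-compliance with treatment regimen or study requirements" and "Subjects which have Cholecystitis and it will be operated upon", together with ineligibility, withdrawn consent and loss to follow-up. Protocol 8.8 adds withdrawal when an excluded medication is needed.

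Such reasons need not be balanced. The trial is open label, and by Protocol 8.4 one arm takes a single combined tablet every 12 hours while the other takes ciprofloxacin every 12 hours plus metronidazole every 6 hours. A difference in adherence or refusal is plausible, though the documents do not quantify it. At stake is whether a significant p-value in the Primary Safety section reflects harm or something else.

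**Working it through.** **Which shell measures heading B?** Heading B has three elements: participants, AE as the cause, and permanent discontinuation.

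| Shell | Limited to AEs? | Limited to discontinuation? |
|---|---|---|
| Table 6 | Not stated | Yes, permanence not stated |
| Table 7 (and Table 4 for SAEs) | Yes | No, pooled with treatment change |
| Table 8 | Yes | No, all AEs |

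No row of this table meets both conditions as labelled.

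**How far could other stops move the Table 6 total?** The plan has no discontinuation figure to reproduce. The arm size of 156 comes from SAP 7.1 and the shells. All rates and counts below are assumptions. Each participant is given one cause, so percentages add, and the total row is taken to receive its own p-value, as the layout allows.

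For two arms of equal size, with a and b stops and N = 312, the Pearson statistic without continuity correction is

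X² = N(a − b)² / [(a + b)(N − a − b)].

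*A difference created by other causes.* AE stops 4 v 4 (p=1.00) and other stops 3 v 14 give totals of 7 v 18:

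X² = 312 × 11² / (25 × 287) = 37,752 / 7,175 = 5.26, p=0.022 (0.037 with continuity correction, 0.035 by Fisher's exact test).

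*How often.* The rejection probability is the sum, over all a and b, of Bin(a; 156, pA) × Bin(b; 156, pB) wherever X² exceeds 1.96². With AE stops at 3% in both arms:

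| Other stops | Total | Chance of p<0.05 |
|---|---|---|
| 5% v 5% | 8% v 8% | 4.8% |
| 5% v 10% | 8% v 13% | 30% |
| 5% v 15% | 8% v 18% | 76% |

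A test of AE stops alone, 3% v 3%, rejects in 4.5%. The result depends on the size of the gap: totals of 10% v 14% give 19%, and 10% v 19% give 62%.

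*A difference concealed in the total.* AE stops 12 v 3 give X² = 312 × 9² / (15 × 297) = 25,272 / 4,455 = 5.67, p=0.017. With other stops of 5 v 14 the totals are 17 v 17, p=1.00. In rates, AE stops of 8% v 2% are detected in 71% of trials by an AE-only test. The all-cause total detects them in 43% if other stops are 5% in both arms, and in 6% if they are 5% v 10%. These figures describe the total row only.

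**The case against.** Four points deserve weight.

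First, heading B can be read as limiting everything beneath it, so that Table 6 lists only AE causes. That reading is available. It would not simply duplicate Table 7, which pools in treatment changes. But neither the item nor the table states the limit, the neighbouring items do, and the total row is worded without it. On the narrow reading Table 6 comes close to heading B's quantity and is mislabelled. Wording is still needed.

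Second, Protocol 10.2.3 lists reasons for leaving the study, not for stopping study drug. A reader might take the whole list as the causes in Table 6. The documents do not say so. That some of them would enter is a natural inference and no more.

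Third, a reader might infer that the plan could conceal a real excess of AE-caused stops. That is too strong. On the all-cause reading AE would be one of the cause rows, AE-caused stops also count in Table 7, and Protocol 14.2 already tabulates discontinuations due to AEs by treatment and drop-outs with reasons. Nothing makes the Table 6 total the deciding line.

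Fourth, no rule turns a significant total into a claimed safety advantage. The defined endpoint is AE incidence, tabulated separately in Tables 5 and 8, and the cause rows would show what drove the total. This stands and limits the consequence to a misleading label on one p-value.

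**Conclusion.** The mismatch is in the text of both documents: under a heading about AE-caused permanent discontinuation, the first specified comparison is not confined to AEs, and the only AE-specific discontinuation table includes treatment changes. This is more than missing detail, because a test placed under Primary Safety does not measure what its heading names.

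It does not follow that the plan definitely tests all-cause discontinuation. The text is ambiguous, with the total row pointing that way. On that reading, and with equal AE-caused stops, the chance of a significant total rises from about 5% to 30% or 76% as the total in one arm goes from 8% to 13% or 18% against 8% in the other. Those rates are assumed. The open-label design and unequal regimens make an imbalance plausible, not certain.

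Severity is minor: AE and SAE incidence are unaffected, and other planned tables largely guard against concealment.

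**What to change.** 1. In SAP 8.6 B and Protocol 10.7.6 B, make the tested quantity the number of dosed participants whose study drug was permanently stopped because of an AE, over all dosed participants in the arm. SAP 8.1 already uses dosed participants for safety. Give this quantity its own shell.
2. Define treatment discontinuation, including whether a course that ends at the Day 8 visit (Protocol 12.3.2 allows this for some subjects) counts.
3. Move Table 6, all causes, to the subject disposition summary already planned in Protocol 14.2, as n (%) by reason with no p-value on the total.
4. Keep any progression or surgery that meets the AE or SAE definition in the safety tables. It may be tempting to treat these as efficacy outcomes only, but Protocol 13.1 counts worsening from baseline as an AE and 13.2 counts hospitalization or its prolongation as serious.

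The cost is wording in two documents, one relocated table and one relabelled or new shell. No new data are needed for reasons, since Protocol 10.2.3 already has the reason for withdrawal recorded in the CRF; check that the CRF also separates stopping drug from leaving the study. SAP 8.2 foresees a final SAP before database lock, which is the place for the change.
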